7.1 Antitumor Effect

7.2 Safety/tolerability

8. STATISTICAL CONSIDERATIONS 23

- 8.1 Primary Endpoint
- 8.2 Secondary Endpoints
- 8.3 Sample Size
- 8.4 Patient Accrual and Study
- 8.5 Analysis Plan
- 8.6 Gender and Diversity

- 9. STUDY MANAGEMENT 26**
 - 9.1 Conflict of Interest
 - 9.2 Institutional Review Board (IRB) Approval and Consent
 - 9.3 Required Documentation
 - 9.4 Registration Procedures

- 10 DATA MANAGEMENT AND MONITORING27**
 - 10.1 Adherence to the Protocol
 - 10.7 Amendments to the Protocol
 - 10.8 Record Retention
 - 10.9 Obligations of Investigators

[figure not shown]
- 11 REFERENCES..... 34**

- APPENDICES..... 36**
 - APPENDIX I: FACT-Cx (Version 4) English Version
 - APPENDIX II: FACT-Cx (Version 4) Spanish Version
 - APPENDIX III: FACT-Cx Scoring Guidelines
 - APPENDIX IV: Eligibility Checklist
 - APPENDIX V: Performance Scale
 - APPENDIX VI: FIGO STAGING FOR CERVICAL CANCER

LIST OF ABBREVIATIONS

AE	Adverse Event
CBC	Complete Blood Count
CMP	Comprehensive Metabolic Panel
CR	Complete Response
CT	Computed Tomography
CTCAE	Common Terminology Criteria for Adverse Events
CTV	Clinical Treatment Volume
DLT	Dose Limiting Toxicity
DSMB	Data and Safety Monitoring Board
ECOG	Eastern Cooperative Oncology Group
H&P	History & Physical Exam
IMRT	Intensity Modulated Radiation Therapy
MTD	Maximum Tolerated Dose
NCI	National Cancer Institute
ORR	Overall Response Rate
OS	Overall Survival
PD	Progressive Disease
PFS	Progression Free Survival
p.o.	Per os/by mouth/orally
PR	Partial Response
PTV	Planning Treatment Volume
SAE	Serious Adverse Event
SD	Stable Disease
WBC	White Blood Cells

STUDY SCHEMA

STUDY SUMMARY

Title	A Phase II Study of Image Guided Hypofractionated Radiation Boost Therapy for Definitive Treatment of Locally Advanced Cervical Cancer
Short Title	Image Guided Hypofractionated Radiation Treatment for Advanced Cervical Cancer
Protocol Number	STU 082013-064
Phase	Phase II
Methodology	Patients who are eligible for the study will be prospectively identified, treated using Image Guided Hypofractionated Radiation Treatment and followed for efficacy and toxicity.
Study Duration	Study accrual: 3 years Follow-up: 5 years
Study Center(s)	University of Texas – Southwestern Medical Center
Objectives	The purpose of this study is to determine whether Image Guided Hypofractionated Radiation Treatment is effective in women with locally advanced cervical cancer without increased risk of acute GI or GU toxicity.
Number of Subjects	21
Diagnosis and Main Inclusion Criteria	Inclusion Criteria 
 • Biopsy proven squamous, adenosquamous, or adenocarcinoma of uterine cervix • Willing and capable of consent • FIGO Stage IB2 - IVB, cervical cancer
Study Product(s), Dose, Route, Regimen	Patients enrolled in this study must have received or planned to receive 45Gy of prior external beam radiation therapy. Following completion, patients will receive 28 Gy in 4 fractions using Image Guided Hypofractionated radiation therapy techniques.
Duration of administration	All radiation therapy should be preferably completed within 56 days.
Reference therapy	Image Guided Hypofractionated Radiation Treatment will be compared to standard of care which consists of standard chemoradiation followed by intracavitary high dose rate brachytherapy.

1. BACKGROUND AND RATIONALE

1.1 Disease Background

Locally Advanced Cervical Cancer (LACC)

There will be an estimated 12,300 new cases of cervical cancer diagnosed in the United States in 2013, with one third that number dying from the cancer [1]. While the incidence of cervical cancer in the United States has been gradually declining as a result of widespread screening, outcomes still remain poor for many with cervical cancer. In addition there has been a negligible survival improvement over the past decade. [2] Even with the increased screening in the U.S., 48% of patients still present at an advanced stage [2]. Globally cervical cancer is widespread (no. 3 cancer in women) and lethal (with a mortality incidence ratio of 52%) [3]. Several prospective randomized trials compared concurrent chemotherapy and radiation to radiation alone for advanced cervical cancer and showed substantial improvement in local control and overall survival in the late nineties [4, 5]. As a result, the National Cancer Institute issued a treatment alert in 1999 establishing chemoradiation as the standard of care for advanced cervical cancer. Radiotherapy for cervical cancer currently consists of radiation in the form of external beam delivered over 5-6 weeks of daily therapy followed by or interdigitated with intracavitary or less frequently, interstitial brachytherapy. These procedures remain invasive and require use of supportive medications ranging from general anesthesia in the operating room to a combination of sedatives and narcotics for insertion of the brachytherapy devices. Furthermore, intracavitary brachytherapy delivers dose to a limited volume of tissue around the cervix and may be inadequate for delivering dose to tumors that extend to the pelvic sidewall. As a result, even with the use of chemoradiation, approximately 30% of patients with locally advanced disease will have a locoregional recurrence [5]. These results of best local control for Stage III-IVA cervix cancer of 70% applies to carefully chosen patients in clinical trials. Patients with bulky advanced cervical cancers like the vast majority of patients we see at Parkland (PMH) and UTSW have an inferior local control which is hampered by poor performance status of these patients. In a recent review of patients from 2003-2011 at PMH, the actuarial overall survival for all II-IVa pts was only 34% at 5 years [6]. A significant group of patients had locoregional failure or persistence, presumably due to bulky tumor volume exceeding the limitations of available radiation and chemotherapeutic modalities. Additionally, patients often present with multiple untreated co-morbidities which makes them often unable to undergo standard chemoradiation and brachytherapy often compromising the delivery of adequate radiation dose and hence the tumor local control. Furthermore, current treatments are often unpalatable for many patients because they are either too invasive, inconvenient or inadequate.

The implementation of Intracavitary brachytherapy (which is the most commonly applied form of Brachytherapy in the US) [7] in bulky tumors (esp. Stage IIIB tumors which extend to the pelvic side-wall), results in inadequate dosage to tumor especially at side-wall of pelvis. This occurs because of the rapid falloff of radiation dose from intracavitary brachytherapy sources which may explain the relatively high rate of local failure in bulky stage III cervical cancers.

More advanced methods of delivery are available, like Image Based high dose rate Brachytherapy with the Europeans being the innovators in this area. Under the aegis of the GEC-ESTRO group many new frameworks for HDR Cervix brachytherapy have been introduced with emphasis on volumetric assessment of dose to cervix CTV recommended to be based on MR imaging [8]. The most updated French Multicentric experience of over 600 patients with cervical cancer comparing 2D with 3D image based intracavitary brachytherapy

showed that in the advanced cervical cancer patients (mostly stage II; as IIIB were only 25% of group) local recurrence was still 25%. They did not break up recurrence by stage.[9]

For the bulkier tumors, in order to improve tumor control, interstitial brachytherapy is recommended by some. These are more invasive procedures and involve transperineal Interstitial needle placement into cervix tumor with General anesthesia, hospital inpatient stay, extensive support and involvement of considerable resources and provider-hours. Even with these invasive procedures, the best results provide 60-65% local control at 2-3 years for all stages [10, 11]. This is an important problem, since locally advanced cervical cancer continues to recur despite current treatments and more effective, less toxic and more convenient treatments are necessary.

The Vienna group has pioneered a combined Intracavitary- Interstitial technique which requires Intra-operative MRI suite which is impractical in the US setting and particularly in the county hospital setting which we work in.[12]

Their best results with IIIB disease are using 3D image based hybrid version of Intracavitary/interstitial brachytherapy using a customized ring applicator with needles achieved a local control of 86% for IIIB cancer .[13]This process is very resource intensive and requires interstitial MR guided-Brachytherapy expertise which may not be available in most US centers.

We propose Precise Image Guided Hypofractionated Radiation treatment building on our experience with prostate cancer which has a similar anatomic profile to bulky cervical cancer albeit involves slightly larger volume of treatment. [14] Brachytherapy is very effective in delivering dose to fixed volume within close proximity cervix, while Image Guided Hypofractionated Radiation Treatment can be shaped to larger patient specific tumor volumes. We will use existing HDR brachytherapy regimens and modified Brachytherapy tumor targets to deliver precise doses of SABR in 4 fractions of 7Gy each delivered over 2-3 weeks.

It is predicted that the dose limiting toxicity from this treatment will likely relate to Grade 4 bladder/urethral dysfunction (e.g., ulceration, bleeding, pain, narrowing and frank stricture) and rectal damage (ulceration, bleeding, chronic inflammation, and pain or fistula) causing emergent and life-threatening situation requiring admission. Based upon the best results of Vienna combined Intracavitary-Interstitial Brachytherapy, we predict that with more complete radiation dose delivery to these tumors using Image Guided Hypofractionated Radiation Treatment, we will be able to increase the local control from 65 to 85%at 2 years. A safety-lead in will be used for the first 6 patients to see if we have any unexpected Grade 3,4 toxicity within first 90 days after commencement of Image Guided Hypofractionated Radiation boost.

1.2 Image Guided Hypofractionated Radiation Treatment

Stereotactic radiosurgery generally refers to a procedure designed to treat deep-seated brain tumors or abnormalities, and is commonly performed on a specialized machine, such as the Gamma Knife. This procedure involves immobilizing the patient (cranial halo), affixing a stable 3-D coordinate system (fiducial box and head frame), performing high resolution imaging (CT or MRI), registering the images to the coordinate system using a computer, virtually simulating delivery of very focal and conformal dose profiles of radiation with steep dose gradients toward normal tissue, and finally carrying out the treatment with millimeter accuracy. Typically very high doses of radiation (15-40 Gy) are given in a single treatment with this technique. Any adjacent normal tissues that receive this dose may be significantly damaged, thus the requirement for very conformal treatments with rapid dose fall-off. An alternate strategy has

been to divide total radiation dose into two or three fractions, still with fairly large dose per fraction (6-10 Gy), attempting to decrease adjacent normal tissue toxicity. These fractionated techniques are referred to as 'stereotactic radiotherapy,' and are carried out with hope that surrounding normal tissue will tolerate the treatment as a result of relatively more successful sublethal damage repair as compared to tumor.

Translation of the stereotactic radiosurgery and radiotherapy concepts to extracranial sites has not been straightforward.[15] With brain treatments, the skull serves as an excellent surface to rigidly couple the immobilization frame using stainless steel pins under local anesthesia. Such is not the case for extracranial sites. Inherent motion, such as the heart beating, lungs expanding and emptying, and bowels churning, results in movement of potential targets. In addition, the external surface anatomy does not have structures amenable to rigid fixation to a frame. In 1994, Lax, et al, from the Karolinska Hospital in Sweden reported on the development and testing of an extracranial frame that incorporated a fiducial stereotactic coordinate system along its side panels[16]. The system used vacuum pillows to make contact with three sides of the patient (maximizing surface area of contact) and correlation of external anatomical reference points on the sternum and calf for immobilization. To decrease respiratory excursion, an abdominal press was employed forcing the patient to perform relatively more chest wall rather than diaphragmatic breathing. A formal verification of reproducibility study was carried out, and target motion was reduced to within 0.5 cm in the axial plane and 1.0 cm in the caudal/cephalad plane. With this degree of accuracy (compared to 0.05 cm target position accuracy for the Gamma Knife), stereotactic radiosurgery could not be performed; however, they did set up a program treating patients with extracranial stereotactic radiotherapy.

Image Guided Hypofractionated Radiation Treatment is a new therapeutic paradigm for treating localized tumors outside of the central nervous system and involves delivering very high doses of focused radiation using unique beam arrangements and special immobilization equipment. As already demonstrated in lung and liver cancers, these treatments offer hope for improved local control of cancers that may translate into gains in survival especially for smaller early stage lesions. Image Guided Hypofractionated Radiation Treatment employs daily treatment doses dramatically higher than typical for conventionally fractionated radiation therapy (CFRT). In turn, it is incorrect to assume that Image Guided Hypofractionated Radiation Treatment radiobiology is similar to historical CFRT. Indeed, a unique biology of radiation response for very large dose per fraction treatments is being appreciated both in terms of tumor control as well as normal tissue consequences translating into unique clinical outcomes. For example, local control with CFRT in early stage lung cancer is consistently reported below 50% while several series using SABR show local control around 90% [17]

Image Guided Hypofractionated Radiation Treatment has been defined by the American College of Radiology (ACR) and American Society of Therapeutic Radiology and Oncology (ASTRO) to involve the use of very large dose per fraction [18]. Typically, only 1-5 fractions are used for Image Guided Hypofractionated Radiation Treatment depending on the tolerance of adjacent or intervening normal tissues. Linear structures (like the spinal cord) and tubular structures (like the bowels) are commonly called "serially functioning tissues" akin to series electrical circuits because their function is disrupted if there is a defect anywhere along their pathways.[19, 20] It has been shown that serial functioning tissues are less tolerant to Image Guided Hypofractionated Radiation Treatment than so-called "parallel functioning tissues" like the peripheral lung and liver. In response, typically more fractions are employed (e.g., five fractions rather than one) when serially functioning tissue cannot be avoided.

1.3 Rationale

1.3.1 Previous experience with Image Guided Hypofractionated Radiation Treatment for Gynecological Tumors and Cervix cancer

There is limited experience in the literature utilizing Image Guided Hypofractionated Radiation Treatment for primary cervix cancer. Most of the series are for recurrent or persistent gynecological tumors in pelvis or retroperitoneum [21-25]. These have been successful as an alternative to brachytherapy with comparable toxicity. For primary cervix cancers, while intracavitary brachytherapy provides the best results, there are a group of patients unable to have standard brachytherapy for whom pilot studies of Image Guided Hypofractionated Radiation Treatment have been performed [21, 26][27, 28]. These have been able to demonstrate in small patient samples that Image Guided Hypofractionated Radiation Treatment for cervix cancer can be delivered safely in the clinic but systematic followup and local control data are unavailable in some of the recently published studies. There have also been dosimetric studies showing feasibility of Image Guided Hypofractionated Radiation Treatment for primary cervix cancer as a replacement for brachytherapy with equivalent dose parameters [29-31]. We will base our planning on our previous experience with Image Guided Hypofractionated Radiation Treatment for prostate cancer which has similar central pelvic location like cervix cancer [14, 32] In that patient cohort, we demonstrated that Linac based Image Guided Hypofractionated Radiation Treatment could be safely administered for men with prostate cancer in five fractions without acute dose limiting toxicity with complete PSA response in this Phase I study.

1.3.2 Current protocol

In the case of treating cervical cancer, the rectum and bowel is an adjacent serially functioning tissue while the bladder is a parallel functioning tissue directly anterior to the cervix. The cervix will be delineated with fiducial CT-visible markers in 4 quadrants and if required the lower end of any intravaginal component will also be marked.

The volume to be treated by Image Guided Hypofractionated Radiation Treatment will be similar to the volume recommended by the GEC_ESTRO group for Intracavitary/Interstitial brachytherapy and with identical fractionation to have a frame of reference for this unique approach to cervix cancer.

2. STUDY OBJECTIVES

2.1 Primary Objective

The primary objective is to improve primary tumor local control of eligible LACC using Image Guided Hypofractionated Radiation Treatment as the mechanism for delivering boost therapy to 85% at 2 years post treatment.

A phase I safety lead-in will be performed as described in section 8.

For the safety lead-in phase, acute grade ≥ 3 gastrointestinal (GI) toxicity (perforation, obstruction, bleeding, ulceration, necrosis, proctitis and diarrhea requiring elective or urgent hospitalization) and grade ≥ 3 genitourinary (GU) toxicity (cystitis, hematuria and incontinence requiring elective or urgent hospitalization) within 90 days from the commencement of Image

Guided Hypofractionated Radiation Treatment boost will be assessed. Toxicity will be graded according to the Common Terminology Criteria for Adverse Events (CTCAE) version 4.

2.2 Secondary Objectives

- 2.2.1 To determine the acute (< 90 days) and late (90-365 days) grade ≥ 3 GI and GU toxicity as assessed by CTCAEv4 from the commencement of Image Guided Hypofractionated Radiation Treatment boost.
- 2.2.2 To determine the patient reported quality of life (FACT-CX)

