6.3 Follow-up Procedures

Patients will be followed for 5 years after completion of treatment or until death, whichever occurs first. Patients removed from treatment for unacceptable adverse events will be followed until resolution or stabilization of the adverse event. Patients will be seen at clinic at 1 month, 3 months, 6 months, 12 month, 18 month, 24 month, then annual for 3 more years post-therapy for evaluation of disease progression as well as radiation toxicities.

- For the purposes of this protocol completion of therapy will be considered the day on which the fourth and final fraction of Image Guided Hypofractionated Radiation Treatment is delivered
- Any visit between one month and four month after the completion of therapy will be considered the three months visit
- Any visit between five months and eight months after completion of therapy will be considered the sixth month follow up
- Any visit between ten months and fourteen months after the completion of therapy will be considered the one year follow up
- Follow ups beyond one year can be scheduled \pm 2 month for each time point.

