8.2 Secondary Endpoints

The secondary objectives are to:

- Determine the late grade ≥ 3 GI and GU toxicity as assessed by CTCAE v4 at 91-365 days from the start of protocol treatment. *This will be summarized using a proportion and a 95% confidence interval.*
- Measure Cervix cancer specific patient reported QOL at 6 time points using FACT-CX validated measurement tools with our VTOC system

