8.5.2 The Analysis of Severe Late GU/GI Toxicity

This analysis will be carried out when each patient has had at least 90 days (i.e., 3 months) of follow-up after the end of the acute period. The time to the occurrence of severe late GU/GI toxicity is defined as the time interval from start of protocol treatment to the date of onset of grade 3-5 GU/GI toxicity. A Kaplan-Meier curve will be used to estimate the time to late toxicity. The time analysis for recording severe late GU/GI toxicity for this protocol will be limited to 180 days from after completion of protocol therapy, although every effort will be made to document any late toxicity during subsequent follow-up. If no such toxicity is observed before the time of the analysis, the patient will be censored at the time of the analysis.

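### Late grade 3+ GI/GU toxicity is estimated only to day 365 (180 days after therapy in 8.5.2), so no named endpoint gives late harm at the 2-year horizon of the primary benefit

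*Combined protocol and SAP*

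**What the plan says.** Three sections put a window on severe late GI/GU toxicity.

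- Section 2.2.1 has "late (90-365 days) grade ≥ 3 GI and GU toxicity as assessed by CTCAEv4", counted from the start of the boost.
- Section 8.2 has the endpoint "at 91-365 days from the start of protocol treatment" and adds: "This will be summarized using a proportion and a 95% confidence interval".
- Section 8.5.2 starts its clock at the start of protocol treatment and says that the time analysis "will be limited to 180 days from after completion of protocol therapy". It allows the analysis once every patient has 90 days beyond the acute period. For events after the limit it offers recording only: "although every effort will be made to document any late toxicity during subsequent follow-up".

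Follow-up runs much longer. Section 6.3 schedules visits at months 1, 3, 6, 12 and 18, and then "24 month, then annual for 3 more years post-therapy for evaluation of disease progression as well as radiation toxicities". Section 6.3.1 requires a toxicity assessment at each of them. The primary objective (2.1) and the sample size (8.3.1) judge local control at 2 years, 85% against 65%.

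Two other sections touch later toxicity. Section 8.5.1 plans acute and late rates with exact binomial intervals, a Kaplan-Meier estimate of time to toxicity, and annual reports that include toxicity by frequency and severity. Section 10.3 keeps watching the unacceptable-toxicity rate during follow-up against 30%.

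**The concern.** Benefit and harm are on different horizons. Local control is claimed at 2 years, while the endpoint that carries late severe toxicity stops at 1 year, and its time-to-event analysis stops at about half a year. Of the nine scheduled visits (months 1, 3, 6, 12, 18, 24, 36, 48 and 60), five fall after month 12. They collect toxicity data to which no named endpoint assigns an estimate.

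A report that followed the plan could set a 2-year control rate beside a late-toxicity rate ending at day 365. A reader weighing the two would tend to take the second as the price of the first. Any first severe late event after day 365 would be absent from that figure, even though the trial had recorded it. Section 1.3.1 notes that some recent studies of this technique in cervix cancer lack systematic follow-up, so longer-term harm is something this trial is placed to supply.

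**Working it through.** **1. The plan's own figure.** The documents give no sample size, precision or expected rate for late toxicity. The only design figure is 21 patients, which rests on local control (8.3.1: 65% against 85% at 2 years, two-sided 0.10, 80% power, 2 years' accrual, 2 years' follow-up, exponential). Hazards are −ln(0.65)/2 = 0.2154 and −ln(0.85)/2 = 0.0813 per year, ratio 0.377. The event probability under the alternative is 0.215, so the expected count per patient under the null hazard is 0.215/0.377 = 0.570. The one-sample log-rank formula gives N = (1.645 + 0.842·√0.377)² / (1 − 0.377)² / 0.570 = 21.1; a cube-root version gives 19.8. The stated 21 is reproduced closely, and nothing in it depends on the toxicity window.

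**2. The windows side by side.**

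| Item | Clock starts | Ends |
|---|---|---|
| Late objective (2.2.1) | start of boost | day 365 |
| Late endpoint (8.2) | start of protocol treatment | day 365 |
| Late time analysis (8.5.2) | start of protocol treatment | 180 days after completion |
| Visits with toxicity assessment (6.3, 6.3.1) | completion of therapy | month 60 |
| Primary benefit (2.1) | after treatment | 2 years |

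**3. Time covered.** The late window is 365 − 90 = 275 days. From day 90 to 2 years is 730 − 90 = 640 days, so it covers 275/640 = 43%. To 5 years it is about 1,826 − 90 = 1,736 days, or 16%. These are shares of days, not of events. For 8.5.2, section 1.1 has the boost delivered over 2–3 weeks, so 180 days after completion is about day 194 to 201 from the start of the boost. That is 104 to 111 of the 275 days (38% to 40%).

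**4. Illustration of size (assumptions: constant hazard from day 90, no deaths).** If q is the true late rate from day 90 to day 730, then h = −ln(1 − q)/640 and the rate seen by day 365 is 1 − exp(−275h) = 1 − (1 − q)^(275/640).

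- q = 10%: 4.4% seen; 0.9 of 2.1 expected patients among 21.
- q = 20%: 9.1% seen; 1.9 of 4.2.
- q = 30%: 14.2% seen; 3.0 of 6.3.

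**5. Sensitivity to timing and death.** With a Weibull hazard from day 90, the exponent becomes (275/640)^k. Over the same three values of q, k = 0.7 (front-loaded) captures about 57–60% of the 2-year rate, and k = 1.5 (back-loaded) about 29–32%. For death, take the 34% 5-year survival that section 1.1 reports for local stage II–IVa patients as an exponential hazard (assumption), −ln(0.34)/5 = 0.216 per year. In the q = 20% case the share of 2-year events captured rises from 46% to 50%, and the share of 5-year events from 20% to 28%.

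**6. Precision.** Exact 95% intervals at n = 21 are 0–16.1% for 0 events, 0.1–23.8% for 1 and 1.2–30.4% for 2. At 34% survival, about 0.34 × 21 = 7 patients would be alive at 5 years.

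**The case against.** The strongest reply is that later events are not lost. Section 8.5.2 asks that they be documented. The Kaplan-Meier curve in 8.5.1 has no stated end, so it may well run to last follow-up, and the annual toxicity tables have no window either. Section 10.3 requires an unacceptable-toxicity rate to be kept up during follow-up, with recommendations about reporting if it passes 30%. All of this stands. A reader might infer that severe toxicity after year 1 is used nowhere or would go unreported; the documents do not support that. What the reply does not supply is a late estimate. The 8.5.1 curve states no grade, organ system, time origin or horizon. The late rate in 8.5.1 sets no window of its own, and reading it by the day-365 definition is the natural inference, though still an inference. The 10.3 rate also takes in neurological and other toxicity, and passing 30% leads to a review.

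Second, a reader might call the late rate biased. It is not biased for the interval it is labelled with. The problem is that this interval does not match the horizon of the benefit.

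Third, section 1.1 predicts dose-limiting events such as "narrowing and frank stricture", and a reader might infer that the plan itself expects them after the first year. It does not say so: the text describes grade 4 emergencies requiring admission and goes on to a 90-day safety lead-in. No section gives the timing of late events.

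Finally, with 21 patients any later estimate will be imprecise. That limits what the 5-year figure can bear. It does not justify leaving the 2-year figure out.

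**Conclusion.** The point holds as a gap in a secondary endpoint. The plan pre-specifies no late grade 3+ GI/GU estimate at 2 years or beyond, although it collects the data and claims its benefit at 2 years. The late rate would therefore understate the accompanying harm if any patient's first severe late event falls after day 365, and would equal it otherwise. The 180-day limit in 8.5.2 also conflicts with day 365 in 2.2.1 and 8.2, and the time origins differ.

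The size is unknown, because the documents give neither a late event rate nor its timing. Under the constant-hazard illustration without deaths, somewhat under half of the 2-year rate is seen by day 365. Over the Weibull shapes tried the share runs from 29% to 60%, and allowing for death moves it up modestly. The definitional gap does not depend on these figures. The primary test and the 21 patients are unaffected, so this is a cheap improvement and not a flaw in the main comparison.

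**What to change.** Amend 2.2.1, 8.2 and 8.5.2 together; changing only the first two would leave the 180-day limit contradicting the new figures.

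- Use one time origin and one first day of the late period in all three sections.
- Remove the 180-day limit from the analysis in 8.5.2, and count events by date of onset.
- Keep the 1-year late rate.
- Add the cumulative incidence of first grade 3+ late GI/GU toxicity at 2 years, with a 95% interval and death without toxicity as a competing event.
- Give the 5-year cumulative incidence as descriptive, with the number still at risk, because few of the 21 patients may remain.

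The cost is wording in the objective and analysis sections and one more table. The visits in 6.3 already supply the data, so no visit, procedure or patient is added. The drawbacks are that the reported late rate can only stay equal or rise, that the later estimates will have wide intervals, and that the 5-year figure arrives well after the primary result.
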